### **6.2. Modifications from the Approved Statistical Analysis Plan**

Not applicable. There are no previous approved SAPs.

### **6.3. Modifications from the Approved DMC Charter**

None.

## 7. ANALYSIS SETS

### 7.1. Efficacy Analysis Sets

The Randomized Set is defined as all randomized participants. Unless specified otherwise, a participant will be allocated to their randomized treatment in this analysis set.

The Full Analysis Set (FAS) is defined as all randomized participants who initiated IP (brexanolone or placebo). Unless specified otherwise, a participant will be allocated to their randomized treatment in this analysis set.

The Per-Protocol Set (PP) is defined as all randomized participants not having any major protocol deviations. Unless specified otherwise, a participant will be allocated to their randomized treatment in this analysis set.

### 7.2. Safety Analysis Set

The Safety Set will include all participants who initiated IP (brexanolone or placebo). Unless specified otherwise, a participant will be allocated to the treatment actually given in this analysis set.

## 8. STATISTICAL ANALYSIS

### 8.1. General Considerations

Unless otherwise specified, continuous endpoints will be summarized with n, mean, standard deviation (SD), median, minimum (min) and maximum (max). The min and max will be reported with the same number of decimal places as the source (raw) data. Mean and median will be reported to 1 decimal place more than the source (raw) data and standard deviation will be reported to 2 decimal places more than the source (raw) data, but no more than 4 decimal places. Any values that require transformation to standard units (metric or SI) will be converted with the appropriate corresponding precision.

Categorical variables (eg, presence of an AE) will be summarized using counts and percentages. Percentages will be presented to 1 decimal place unless otherwise specified.

All participant data, including those derived, that support the tables and figures will be presented in the participant data listings. Some data may be presented only in participant data listing with an underlying table or figure; these will be indicated in relevant sections below.

All summaries will be provided by treatment – either by treatment assigned at randomization, or actual treatment received. Actual treatment is defined as:

- Brexanolone – if the participant was exposed to brexanolone;
- Placebo – if the participant received placebo and not a single dose of brexanolone.

For the purpose of all safety and efficacy analyses, baseline is defined as the last non-missing measurement on or prior to the initiation of IP, unless stated otherwise.

P-values will be reported to four decimal places, with p-values less than 0.0001 reported as “<0.0001”. P-values larger than 0.9999 will be reported as “>0.9999”.

#### 8.1.1. Definition of Study Day

For the purpose of the efficacy and safety data summaries, Study Day 1 is defined as the date of first dose of study treatment. For visits (or events) that occur on or after the date of first dose of study treatment, Study Day is defined as:

(date of visit [event] – date of first dose of study treatment + 1).

For visits (or events) that occur prior to the date of first dose of study treatment, Study Day is defined as:

(date of visit [event] – date of first dose of study treatment). There is no Study Day 0.

#### 8.1.2. Visit Windows

Visit windows are defined in [Table 2](#). It is noted that certain specific endpoints might have slightly different analysis visit rules. If an endpoint will be analyzed using the visit windows, as specified in the corresponding sections of the applicable endpoints, all assessments within the window, regardless if the assessment is scheduled or unscheduled, will be included. A

participant's individual analysis visit window could potentially contain more than 1 visit. In the event of multiple visits falling within an analysis window, the latest data will be used.

The summary by analysis visit will use the "analyzed records" only – at most one per participant within each window. The data not flagged as the "analyzed record" will be included in listings. A visit that does not fall under any analysis window will remain in the database and will be included in the listings. The visit window does not apply to the baseline assessment.

**Table 2: Visit Windows**

Scheduled Visit	Assessment Window	Analysis Visit Window	Study Day
V2	0 to 12h	>0 to $\leq$ 12h	1
V3	12h to 24h	>12h to $\leq$ 24h	1
V4	24h to 36h	>24h to $\leq$ 36h	2
V5	36h to 48h	>36h to $\leq$ 48h	2
V6	48h to 60h	>48h to $\leq$ 60h	3
V7	60h to 72h	>60h to $\leq$ 72h	3
Day 5 (V8)	Day 5	>72h to Day 5	3-5
Day 7 (V9)	Day 7	$\geq$ Day 6 to Day 10	6-10
Day 14 (V10)	Day 14	$\geq$ Day 11 to Day 17	11-17
Day 28 (V11)	Day 28	$\geq$ Day 25 to Day 31	25-31

Because endpoints are collected with different assessment schedules, some endpoint specific rules will be used:

- The clinical status assessed by RASS, and CAM-ICU in situations where RASS indicates appropriate subject alertness, will be administered daily and therefore will be windowed daily, from Day 1 through the end of study per-participant. If there is more than one assessment time point within the same day, the later assessment(s) will be used in the analysis.
- Hematology/Chemistry will be windowed according to the scheduled visits in the Protocol (Figure 1, page 11 – Visits 2 through 11). If there is more than one assessment within the scheduled visit, the later assessment will be used in the analysis.
- Vital signs will be windowed using the 12-hour interval as presented in [Table 2](#) above, up to Hour 72 (i.e., Visits 2 through 7). Starting from Day 5, it will be windowed daily, with the exception that Day 5 will be windowed as 72 hours –

Day 5. If there is more than one assessment within the same windowed time interval, the later assessment will be used in the analysis.

- Coagulation data is collected at Screening (Baseline), Visit 6, and Visit 9. Visit 6 will be windowed as 42 hours to 72 hours, and Visit 9 will windowed as 72 hours to Day 10.  
[REDACTED]  
[REDACTED]
- ECG is collected at Screening (Baseline), Visit 6, and Visit 10. Visit 6 will be windowed as 42 hours to 72 hours, and Visit 10 will windowed as Day 11 to Day 17.  
[REDACTED]

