**12.1.6.2. Visit 2 (Hour 0) through Visit 9 (Day 7)**

Hematology and clinical chemistry panels are to be recorded daily; panels collected per standard of care may be used. Additionally, coagulation parameters should be recorded at the time points indicated in [Figure 1](#).

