## 8.4. Safety Analysis

Safety and tolerability of brexanolone will be evaluated by adverse events, concomitant medication usage, changes from baseline in vital signs, [REDACTED], clinical laboratory evaluations, RASS, CAM-ICU, and 12-lead ECG. Safety data, including adverse events of special interest (AESI), will be listed by participant and summarized by treatment group. All safety summaries will be performed on the Safety Analysis Set using actual treatment received. Assessments will be mapped to windows, with the choice of the record following the same rule as described in Section 8.1.2.

The safety endpoints and variables considered in the summary tables for this study are summarized in [Table 3](#).

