**Table 4: Summary of Clinical Laboratory Analytes**

Biochemistry	Renal Panel: glucose, calcium, phosphorus, blood urea nitrogen, creatinine, sodium, potassium, chloride, bicarbonate Hepatic Panel: albumin, alanine aminotransferase, aspartate aminotransferase, total bilirubin, direct bilirubin, indirect bilirubin, alkaline phosphatase, total protein, lactate dehydrogenase, gamma glutamyl transferase, c-reactive protein
Hematology	red blood cell count, hemoglobin, hematocrit, white blood cell count (i.e., leukocytes) with differential, platelet count, erythrocyte sedimentation rate
Coagulation	Activated partial thromboplastin time, prothrombin time, and international normalized ratio (INR)

For the laboratory results that is “ $<$  or  $= x$ ”, where  $x$  is a number as collected in the data, the numeric part of the result will be used in the calculation in the summary tables. The same is true if the result is presented as below limit of quantification (BLQ) and a lower limit of quantification (LLOQ) value is provided – LLOQ value will be used for calculation in the summary tables. The actual results as collected will be presented in the listings. The analysis summary will be performed for the scheduled laboratory values only. The unscheduled laboratory values will be presented in the listings.

All statistical analyses of laboratory values will be performed using SI units. Numerical values and change from baseline values will be summarized by actual treatment group at each windowed visit. If a normal range is provided for the parameter, the out-of-range values will be flagged as low or high, where applicable, in the participant data listings. Shift tables will also be generated.

The number and percentage of participants with potentially clinically significant (PCS) values will be provided in separate listings in hematology, serum chemistry, and liver function tests. PCS values will be identified for specific laboratory parameters as outlined in [Table 5](#). The summaries will be based on all post-baseline values, including both scheduled and unscheduled data. Percentages for PCS tables will be based on the number of subjects contributing observations.

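### Hematology and chemistry are recorded once a day but windowed by visits whose only stated windows to Hour 72 are 12 hours wide, so each early by-visit summary holds about half the participants.

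*SAP*

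**What the plan says.** **Collection.** For Visit 2 (Hour 0) through Visit 9 (Day 7), Protocol 12.1.6.2 states: "Hematology and clinical chemistry panels are to be recorded daily; panels collected per standard of care may be used". Routine ICU draws may serve, so draw time need not follow the infusion clock.

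**Windowing.** SAP 8.1.2, in the endpoint-specific rules under Table 2, states: "Hematology/Chemistry will be windowed according to the scheduled visits in the Protocol", and points to Protocol Figure 1 and Visits 2 through 11. Table 2 gives V2 to V7 as six consecutive 12-hour windows covering 0 to 72 hours. V8 then runs from after Hour 72 to Day 5, and V9 covers Days 6 to 10. The records analysed are "at most one per participant within each window", the latest being kept.

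**Use.** SAP 8.4 applies this to all safety data: "Assessments will be mapped to windows, with the choice of the record following the same rule as described in Section 8.1.2". For laboratory data, SAP 8.4.3 adds: "Numerical values and change from baseline values will be summarized by actual treatment group at each windowed visit".

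**Other measures in the same list.** RASS and CAM-ICU "will be administered daily and therefore will be windowed daily, from Day 1 through the end of study per-participant". Coagulation and ECG at Visit 6 get a widened window of 42 to 72 hours. Hematology and chemistry get no comparable adjustment.

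**The concern.** A measure taken every 24 hours cannot fill slots 12 hours wide. Which slot of each pair (V2 or V3, V4 or V5, V6 or V7) a participant fills depends on when the infusion began relative to the routine draw. The by-visit table would then alternate between two groups of participants. A rise or fall from one visit to the next could reflect who is in the slot as much as what happened to them.

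The affected period is the infusion and the hours just after it. Laboratory change from baseline is a named safety endpoint (SAP 4.2). Protocol 9.2.1 notes that the solubilizer may accumulate when renal function is reduced. Protocol 10.1 says placebo has the same formulation without the active ingredient. An effect of the vehicle would therefore be common to both arms and would show mainly as change over time, which is the view that alternating slots obscure. The study also stopped early (SAP 6.1), so participants per slot are scarce.

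**Working it through.** The documents give no figure for laboratory records per window, so there is none to reproduce.

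**Inputs**
- One panel per 24 hours through Day 7: Protocol 12.1.6.2.
- Six 12-hour windows to Hour 72: SAP Table 2.
- At most one record per participant per window: SAP 8.1.2.
- About 100 participants planned, so about 50 per arm: SAP 5.2. Actual enrolment is not given.

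**Slot count**
- Windows: 72 / 12 = 6. Daily panels: 72 / 24 = 3. Expected fill: 3 / 6 = 50%.
- At the planned size: 50 × 0.5 = 25 per arm per slot.
- With equal spread, the standard error is proportional to 1/√n, so the ratio to full daily windows is 1/√0.5 = 1.41.

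**Sensitivity to irregular draw times.** A simulation of 200,000 participants took the infusion start as uniform relative to the daily draw and let the draw time vary. These are assumptions, not facts from the documents. Overlap is the share of participants present in either slot who are present in both.

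| Draw pattern | Fill of each 12-h slot | Overlap of adjacent slots | Overlap of V2 and V4 | Fill of each 24-h window |
|---|---|---|---|---|
| Exactly every 24 h | 50% | 0% | 100% | 100% |
| SD 1 h | 50% | 2% | 83% | 98% |
| SD 2 h | 50% | 5% | 68% | 95% |
| SD 4 h | 50% | 10% | 46% | 91% |
| Random time in each 24-h period | 50% | 0% within a period, 33% across | 33% | 100% |
| Every 12 h | 100% | 100% | 100% | 100% |

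The 50% fill does not depend on how regular the draws are. What does change is how cleanly the slots separate. With exact spacing V2, V4 and V6 hold one group and V3, V5 and V7 the other; with irregular draws the groups mix somewhat. At SD 4 h the standard error ratio is √(0.906 / 0.499) = 1.35, against 1.41 with exact spacing.

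**Uneven starts.** If every infusion began in the 12 hours before the routine draw, V2, V4 and V6 would be full and V3, V5 and V7 empty. Only panels about every 12 hours would fill all six slots.

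**The case against.** **The laboratory rule cites Figure 1, not the 12-hour windows.** The next rule, for vital signs, does cite them: "Vital signs will be windowed using the 12-hour interval as presented in" Table 2. If Figure 1 marks panels at one visit per day, the intended rule may already be close to daily. This stands as a limit on certainty. Against it, the SAP names all of Visits 2 through 11, SAP 8.4 maps safety data to windows, and no other window is defined for V2 to V7. If Figure 1 does mark only some visits, the rule should say which, with windows wide enough for a routine daily draw.

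**ICU patients may have more than one panel a day.** They may, but Protocol 12.1.6.3 asks for additional standard-of-care panels only from Day 8. Their use is also unsettled: SAP 8.1.2 admits unscheduled records, while SAP 8.4.3 says "The analysis summary will be performed for the scheduled laboratory values only".

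**The summaries are descriptive, and safety signals are caught elsewhere.** This stands. PCS counts use all post-baseline values, scheduled or not, liver thresholds are assessed at any time after baseline, and clinically significant results become adverse events. Change from each participant's own baseline also limits how far different membership can distort adjacent means.

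**Stronger readings that the documents do not support.** A reader might infer that differences between arms are artefacts. Draw timing should not depend on arm in a blinded randomized trial, so a within-slot comparison is less precise but not biased in expectation. A reader might take 25 per arm, falling to about 12, as the base; 25 per arm is the size of the cancelled interim analysis, not of the trial. A 05:00 draw with starts between 10:00 and 20:00 would give a 30%/70% alternation and a ratio of 1/√0.3 = 1.83 in the thin slots, but those clock times are assumed and the figures only illustrate.

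**Conclusion.** The mismatch is real and limited in reach. As SAP 8.1.2 reads, by-visit hematology and chemistry summaries in V2 to V7 hold about half of those still followed. Standard errors are about 1.41 times those with daily windows, and adjacent visits summarize largely different people. This assumes one usable panel per day, infusion starts spread evenly relative to the draw, and Table 2 as the definition of the visits. After Hour 72 the feature reverses: V8 and V9 each reduce several daily panels to the latest one. That follows the stated rule and is not an error, though it discards resolution that the daily schedule provides.

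The damage is to precision and to the reading of trends across adjacent visits. The plan should be changed because its own reasoning for RASS and CAM-ICU applies equally here and the change is small. No efficacy result or safety threshold count depends on it.

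**What to change.** In SAP 8.1.2, replace the hematology and chemistry rule with daily windows through Day 7 on one clock throughout. Use either consecutive 24-hour periods from infusion start to Hour 168, or Study Day as already done for RASS and CAM-ICU. Name one record per window in advance.

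Do not switch from hours to Study Day at Hour 72. Study Day is date-based (SAP 8.1.1). For a start between 10:00 and 20:00 and a 05:00 draw, the Study Day 4 panel falls at 57 to 67 hours. It would then belong to both the third 24-hour period and Study Day 4, or leave Study Day 4 empty. If Study Day is chosen throughout, say how Day 1 is handled when that day's only panel preceded the infusion and serves as baseline.

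Keep the Day 14 and Day 28 windows, and state where panels from Days 8 to 10, now inside V9, will go. Reconcile SAP 8.1.2 with 8.4.3 on unscheduled values. Leave PCS counts on all post-baseline records.

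**Cost.** One rule in the SAP and a programming parameter, with no change to collected data. Fill to Hour 72 with 24-hour periods rises from about 50% to 100% with exact 24-hour draws, or 91% to 98% with draw-time SD of 1 to 4 hours. The small loss is coarser time-since-infusion resolution for participants with more than one panel a day.

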## 5.1. Dose Justification

The brexanolone dose regimen to be used in this study (70 mcg/kg/h for 58 hours followed by a 2-hour taper at 35 mcg/kg/h) was chosen for this patient population based on the following considerations:

- Acceptable safety and tolerability profile defined in pivotal nonclinical toxicology studies (see brexanolone Investigator's Brochure for additional details)
- Brexanolone is an endogenous compound that increases during pregnancy, culminating in plasma concentrations of approximately 150 nM at the end of the third trimester. These plasma concentrations are in a similar range as is predicted for an infusion of 70 mcg/kg/h of brexanolone.
- The dosing regimen approximates the total dose and duration approved for the treatment of postpartum depression
- The dosing regimen is intended to simplify dosing in intensive care units and to maintain steady-state plasma concentrations for the maximum amount of time over the course of the infusion in participants with ARDS due to COVID-19
- Participants will be already unconscious prior to or at start of the infusion; therefore, titration (intended to reduce the incidence of dizziness and somnolence in conscious patients) is not considered necessary
- Brexanolone is rapidly cleared; therefore, a short taper is incorporated to slow the decline in plasma concentrations during discontinuation

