## 5. STUDY DESIGN

### 5.1. Overall Design

This is a randomized, double-blind, placebo-controlled study designed to evaluate treatment with brexanolone in approximately 100 participants with ARDS due to COVID-19. Participants and their family or caregivers, clinicians, site staff, and sponsor personnel will be masked to treatment allocation.

Participants with ARDS and SARS-CoV-2 infection who give informed consent (or for whom consent is given by a proxy) and who are currently intubated and receiving mechanical ventilation as part of standard of care or who are on an immediate clinical plan to receive such intervention will be eligible for screening. All participants must have mechanical ventilation in place prior to randomization. Eligible participants will be stratified by age (<70 or  $\geq$ 70 years) and randomized 1:1 within each stratum to receive either brexanolone plus standard of care or placebo plus standard of care.

Participants will receive continued standard of care in addition to a continuous intravenous (IV) infusion of investigational product (IP) – brexanolone or placebo for 60 hours. The infusion must be initiated within 6 hours from the time of randomization. The blinded 60-hour infusion will be administered at a dose of 70 mcg/kg/h for 58 hours followed by a 2-hour taper at 35 mcg/kg/h. Transfer out of the ICU is not an indication to discontinue the infusion of investigational product.

Brexanolone may potentiate the sedative effects of co-administered anesthetics. During IP infusion, if sedation levels are deeper than intended, the dose(s) of sedative anesthetics should be titrated to the desired effect rather than adjusting the dose of IP (see Section 7.4 of the study protocol for additional details).

Dose adjustment is permitted in the event that a participant is experiencing unplanned sedation/somnolence when no longer on any sedating agents or if the participant experiences an intolerable adverse event (AE) determined by the investigator to be related to IP. Details regarding dose adjustment criteria and procedures are provided in Section 7.4 of the study protocol.

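### The Visit 6 ECG window runs 12 hours past the planned end of infusion and keeps the latest record, so an off-infusion QTcF can stand as the on-infusion value

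*SAP*

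**What the plan says.** **Infusion.** SAP Section 5.1: "The blinded 60-hour infusion will be administered at a dose of 70 mcg/kg/h for 58 hours followed by a 2-hour taper at 35 mcg/kg/h". Protocol Section 5.1 gives the reason for the taper: "Brexanolone is rapidly cleared; therefore, a short taper is incorporated to slow the decline in plasma concentrations during discontinuation".

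**ECG schedule and window.** The endpoint-specific rules under SAP Table 2 say: "ECG is collected at Screening (Baseline), Visit 6, and Visit 10. Visit 6 will be windowed as 42 hours to 72 hours". Visit 10 is windowed at Days 11 to 17. Table 2 itself sets the Visit 6 assessment at 48 to 60 hours and its analysis window at more than 48 and up to 60 hours. Hours 60 to 72 belong to Visit 7.

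**Which record is used.** Section 8.1.2 admits unscheduled data: "all assessments within the window, regardless if the assessment is scheduled or unscheduled, will be included". It then says: "In the event of multiple visits falling within an analysis window, the latest data will be used". By-visit summaries use at most one record per participant per window, and unselected records go to listings. Section 8.4 carries this over to safety data: "Assessments will be mapped to windows, with the choice of the record following the same rule as described in Section 8.1.2".

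**What is summarised.** Section 8.4.5 summarises observed ECG values, change from baseline and normal/abnormal status by windowed visit. It also plans counts of potentially clinically significant values and changes (PCS and PCSC) and a summary of maximum QTcF. Neither 8.4.4 (vital signs) nor 8.4.5 says which records feed those counts. For laboratory data, Section 8.4.3 does: "The summaries will be based on all post-baseline values, including both scheduled and unscheduled data".

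**The concern.** Screening precedes the infusion and Visit 10 falls more than a week after it. Visit 6 is therefore the only scheduled ECG that can show an effect on QTcF while the drug is running. If the drug moves QTcF in step with plasma level, a value recorded after the infusion shows less of the effect.

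The window lets this happen in two ways:

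- A single ECG taken between Hours 60 and 72 is labelled Visit 6, and the table does not show that it was off infusion.
- If an on-infusion ECG and a later unscheduled one both fall in the window, the later one is kept and the on-infusion one appears only in a listing.

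Both move the analysed record away from exposure, so any distortion of the brexanolone-placebo comparison is towards no difference. In a safety table that is the unfavourable direction.

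A related gap concerns the outlier counts. Because 8.4.4 and 8.4.5 name no record basis, a programmer could take the general sentence in 8.4 to mean that only the selected record counts.

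**Working it through.** **1. Reproduce the planned infusion length.** 58 h + 2 h = 60 h, as stated. The taper runs from Hour 58 to Hour 60.

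**2. Divide the Visit 6 ECG window (72 - 42 = 30 h).**

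| Segment | Hours | Share of window |
|---|---|---|
| Full rate, 42-58 | 16 | 16/30 = 53.3% |
| Taper, 58-60 | 2 | 2/30 = 6.7% |
| After infusion, 60-72 | 12 | 12/30 = 40.0% |

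Table 2's own Visit 6 window has 0 of 12 hours after the infusion and 2 of 12 (16.7%) in the taper. These are shares of window width. They do not say where ECGs will fall.

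**3. Illustrate the dilution.** The documents give no half-life, so 1, 3 and 9 hours are assumptions. Assume also one-compartment kinetics, steady state by Hour 42, and a QTcF effect proportional to concentration. With k = ln 2 / half-life and C as a fraction of steady state:

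- up to Hour 58: C = 1
- taper: C(t) = 0.5 + 0.5·exp(-k(t - 58))
- after Hour 60: C(t) = C(60)·exp(-k(t - 60))

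Averaging over evenly spread times:

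- A, mean over 48-60 h = [10 + 1 + 0.5(1 - exp(-2k))/k] / 12
- B, mean over 60-72 h = C(60)·(1 - exp(-12k)) / (12k)

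| Assumed half-life | C(60) | C(72) | A (48-60 h) | B (60-72 h) |
|---|---|---|---|---|
| 1 h | 0.625 | 0.0002 | 0.962 | 0.075 |
| 3 h | 0.815 | 0.051 | 0.983 | 0.276 |
| 9 h | 0.929 | 0.369 | 0.994 | 0.606 |

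If every ECG is taken at 48-60 h, the average effect shrinks by 1 - A: 3.8%, 1.7% and 0.6%, or about 1-4%.

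**4. Let a share p of analysed ECGs fall after Hour 60.** Mean = (1 - p)·A + p·B. The documents give no p. Taking p = 10% purely as an example:

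- 1 h: 0.9 × 0.962 + 0.1 × 0.075 = 0.873, a 13% shrinkage
- 3 h: 0.9 × 0.983 + 0.1 × 0.276 = 0.913, 9%
- 9 h: 0.9 × 0.994 + 0.1 × 0.606 = 0.955, 4%

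The size thus turns on p, which the window leaves unchecked, and on the half-life.

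**The case against.** **Only one ECG is scheduled in the window.** Replacing an on-infusion ECG needs a second, later, unscheduled one, and the documents do not say how often that occurs. This stands. It limits how often replacement happens, but a lone late ECG is still labelled Visit 6 without a second record.

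**Endpoint-specific windows are allowed.** Section 8.1.2 says so, and a wider window keeps participants who would otherwise have no value. So the difference from Table 2 is not a contradiction. However, no reason is given for running past the end of infusion, and a separate row keeps the same data.

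**A redacted line follows the ECG rule.** A tie-breaking rule could stand there. On the visible text the general rule governs. A hidden rule for choosing among records would not by itself change a window that ends at Hour 72.

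**A reader might infer a 16-39% loss of effect.** Spreading ECG times evenly over 42-72 h gives mean concentrations of 84%, 70% and 61% of steady state for half-lives of 9, 3 and 1 h. But Table 2 sets the assessment at 48-60 h; 42-72 h is only the analysis allowance. The documents do not support that spread.

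**A reader might infer that the one-record rule governs the PCS counts,** so that the unscheduled vital signs which Protocol Section 12.1.3 requires at an adverse event of special interest drop out. Section 8.1.2 ties the one-record rule to by-visit summaries, and the PCS sentences in 8.4.4 and 8.4.5 name no visit. The basis is unstated, not shown to be one record.

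**A reader might extend the argument to vital signs.** "Vital signs will be windowed using the 12-hour interval as presented in" Table 2, so no reading after Hour 60 can enter Visit 6. The taper is 2 of 12 hours of that one window, and Visits 2 to 5 lie wholly within the planned full-rate period. No change to the Visit 6 vital-sign record is warranted.

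**Conclusion.** The point holds as a minor one. As the visible text stands, an ECG up to 12 hours after the planned end of infusion can be reported as the on-infusion value, or can displace one if a later unscheduled ECG exists. The by-visit QTcF summary can be diluted as a result.

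The expected size is about 1-4% if ECGs are taken when scheduled, and larger only to the extent that analysed ECGs fall after Hour 60. That range rests on assumed half-lives of 1 to 9 hours, one-compartment kinetics, a concentration-proportional effect and the planned infusion times. Interruptions would move the actual end of infusion. The documents give neither a half-life nor the distribution of ECG times, so the true size cannot be stated.

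The affected outputs are descriptive, and unselected records remain in listings. Separately, the record basis for the ECG and vital-sign PCS and PCSC counts, and for maximum QTcF, is an ambiguity that should be closed.

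**What to change.** **SAP 8.1.2, ECG rule.** Define the on-infusion ECG as the last ECG recorded after the start, and at or before the actual end, of the participant's infusion, using recorded infusion times. The lower bound is needed: without it, a participant with no ECG during the infusion would contribute the screening ECG and a change of zero. Summarise ECGs after the actual end of infusion and up to Hour 72 in a separate, labelled row.

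**SAP 8.4.4 and 8.4.5.** State that PCS and PCSC counts, and maximum QTcF, use all post-baseline values, scheduled and unscheduled, as 8.4.3 already does for laboratory values.

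**Cost.** A few sentences and some programming before database lock. Infusion start and end times are already needed for the exposure calculation in Section 8.2.7, so no new data are required. The on-infusion ECG row will have fewer participants, but the late ECGs are still reported in their own row.
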